1.2 Schema

1.3 Schedule of Activities

Measure	Visit 0:	Visit 1:	Visit 2:
	Screening & randomization	Discharge	6-wk postpartum in-person or virtual visit
Informed consent	Х		
Demographics	Х		
Medical history	Х		
Randomization	Х		
Number of inpatient opioids used (MME)		Х	
BPI pain severity		X	
Edinburgh Postnatal Depression Scale			Х
Number of opioids prescribed (MME)		Х	
Opioid prescription refilled (or initially filled if not prescribed at discharge)			Х
Opioid-related side effects		X	

ELECTRON Protocol # 2022H0046

Measure	Visit 0:	Visit 1:	Visit 2:
	Screening & randomization	Discharge	6-wk postpartum in-person or virtual visit
Breastfeeding		Х	Х
Maternal & infant outcomes		Х	Х

2 Introduction

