To evaluate whether non-invasive bioelectronic treatment post-cesarean reduces opioid related side effects, wound disruption and increases rates of breastfeeding	 Opioid related side effects including nausea and constipation Surgical site would disruption/infection Breastfeeding rates at discharge and 6 weeks postpartum Maternal depression score ≥ 13 at 6 weeks postpartum 		

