7.2.7 Reporting Events to Participants

Participants will not be informed about adverse events, serious adverse events, or study-related results unless the PI decides such information should be reported to participants. As noted in Section 7.2, an Edinburgh depression score of 13 or higher, or a value other than 'never' on the Edinburgh question 10 (harming oneself), will be reported to the participant and the clinical provider.

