8.1 Statistical Hypotheses

The primary endpoint is the amount of inpatient opioid consumed post-cesarean measured by total morphine milligram equivalents used. The null hypothesis is that there is no difference in amount of inpatient MME in the non-invasive bioelectrical device intervention group compared to sham device group. The alternative hypothesis is that the amount of inpatient MME in the non-invasive bioelectrical device intervention group is less then MME in the sham device group.

Key secondary endpoints include:

- Worst pain score assessed at discharge measured by presence or absence of moderate to severe pain at 1 week post-discharge, defined as a value of 4 or more on the BPI worst pain in the last 24 hours numeric scale (0 to 10).
- Opioid prescription beyond that prescribed at discharge within 6 weeks postpartum
- Opioids prescribed at discharge
- Opioid side effects, wound complications and breastfeeding rates

For the secondary endpoints, the null hypothesis is there is no true difference between the two groups. The alternative hypothesis is there is a difference between the groups. For the key secondary outcomes, the level of significance will be adjusted for multiple comparisons using the false discovery rate method.⁴¹

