8.4.2 Analysis of the Primary Endpoint

The primary outcome is continuous and defined as MME consumed inpatient post-cesarean not normally

ELECTRON Protocol # 2022H0046

distributed and cannot be transformed to approximate normality, the Wilcoxon test and the Hodges-Lehmann estimators of the median will be reported. If normally distributed then paired t-test and mean with standard deviations will be reported.

Analysis of Secondary Endpoint

Secondary outcomes that are binary or categorical will be reported as a proportion with relative risk and 95% confidence intervals as appropriate. For normally distributed continuous outcomes, least squares means general linear regression will be used to estimate means and 95% confidence intervals. For continuous outcomes that are not normally distributed and cannot be transformed to approximate normality, the Wilcoxon test and the Hodges-Lehmann estimators of the median will be reported.

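### The Edinburgh depression score is collected at 6 weeks but compared between arms only as a cut at 13 or higher; adding a pre-specified analysis of the score is a cheap gain in precision

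*Combined protocol and SAP*

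**What the plan says.** The Schedule of Activities (1.3) lists the "Edinburgh Postnatal Depression Scale" at Visit 2, six weeks postpartum. In section 4 the last row of secondary endpoints includes "Maternal depression score ≥ 13 at 6 weeks postpartum". No mean, change or distribution of the score is listed there or elsewhere.

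The secondary-endpoint text in 8.4.2 then fixes the analysis: "Secondary outcomes that are binary or categorical will be reported as a proportion with relative risk and 95% confidence intervals as appropriate". The same paragraph has a route for continuous outcomes: a general linear model if they are normally distributed and, if they are not and cannot be transformed, "the Wilcoxon test and the Hodges-Lehmann estimators of the median will be reported". Nothing assigns the Edinburgh score to that route.

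Section 7.2.7 uses the same threshold for another purpose. It makes "an Edinburgh depression score of 13 or higher", or a positive answer on the self-harm item, something to be reported to the participant and her clinical provider.

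Depression is not named in the key secondary list in 8.1, whose last item reads "Opioid side effects, wound complications and breastfeeding rates". For secondary endpoints generally, 8.1 states: "The alternative hypothesis is there is a difference between the groups".

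**The concern.** A summed score cut at one point tells the analysis only which side of the line each woman falls on. If the cut lies in the upper tail, most women fall on the same side and differences among them do not count. A moderate shift in mood across the whole group could then appear as an inconclusive relative risk with a wide interval, although the data for a more precise comparison are already held.

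The plan gives no reason why the cut should be the only comparison. The threshold in 7.2.7 is a rule for acting on an individual, which is a different task from comparing arms. Pain is treated differently: section 4 lists the numeric Brief Pain Inventory scores, and the synopsis and 8.1 also define a cut at 4. Depression gets the cut alone. If the score is not pre-specified, an analysis of it added after unblinding would be post hoc.

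**Working it through.** **The plan's own figure.** The only sample size calculation (8.2) is for inpatient MME: mean 42, SD 15, a 20% reduction (8.4), 90% power, 134 in total. With a two-sided 5% level, which the plan does not state, n per arm = 2 × [15 × (1.960 + 1.282) / 8.4]² = 67.01. This reproduces the plan's 67 per arm to within rounding, and power at 67 is 0.900. No corresponding figure exists for depression.

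**Inputs for depression.** From the documents: 67 per arm and a non-directional alternative. Assumed, because the documents are silent: a 5% level, no loss by 6 weeks, a sham rate p at or above 13 of 5% to 25%, and a normal score with a shift across the whole distribution.

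**Formulas.**
- Events if both arms share the rate: 134 × p.
- Efficiency of the cut relative to the full score: φ(z)² / [p(1 − p)], where z is the upper-p normal quantile. Information lost is 1 minus this.
- Power with the score for a shift of d SD: Φ(d√(67/2) − 1.96). For d = 0.4 this is Φ(2.315 − 1.96) = 0.64.
- Power with the cut: the device-arm rate becomes 1 − Φ(z + d), compared with p by the two-proportion z-test. For p = 10%, z = 1.282 and the device-arm rate is 1 − Φ(1.682) = 4.6%, which gives power of 22%.
- 95% CI for a true relative risk of 1: exp(±1.96 × √[2(1 − p)/(67p)]).

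| Assumed rate | Events in 134 | Efficiency | Information lost | Power with cut, 0.4 SD | Power with score, 0.4 SD | 95% CI if true RR = 1 |
|---|---|---|---|---|---|---|
| 5% | 7 | 0.22 | 78% | 15% | 64% | 0.23 to 4.4 |
| 10% | 13 | 0.34 | 66% | 22% | 64% | 0.36 to 2.8 |
| 15% | 20 | 0.43 | 57% | 27% | 64% | 0.45 to 2.2 |
| 20% | 27 | 0.49 | 51% | 32% | 64% | 0.51 to 2.0 |
| 25% | 34 | 0.54 | 46% | 35% | 64% | 0.56 to 1.8 |

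With Fisher's exact test the cut's power at 0.4 SD is lower: 4% at a 5% rate, 12% at 10% and 28% at 25%. At a 0.5 SD shift, power is 19% to 49% with the cut (z-test) and 82% with the score. If 20% were lost by 6 weeks, expected events would be about 5 to 27. The 95% CI for a difference in mean score would have a half-width of 1.96 × √(2/67) = 0.34 SD.

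**Skewed scores.** Simulated negative binomial scores capped at 30, with five parameter sets giving sham rates of 7% to 15% and a 30% lower mean on treatment, gave power of 25% to 47% with the cut and 49% to 71% with Wilcoxon. The information lost was about 48% to 60%. The gain therefore does not depend on normality.

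**Where the gain disappears.**
- Very small effects: at a 0.1 SD shift, power is about 9% with the score and 6% to 7% with the cut. With a 10% lower mean under skewed scores it is about 10% to 12% against 7% to 10%.
- Effect confined to high scorers: if 70% of treated women who would score 13 or more move to 8 to 12 and nobody else changes, power is about 5% to 9% with Wilcoxon and 27% to 66% with the cut (skewed scores, sham means 5.5 and 8). The order reverses.

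**The case against.** The strongest defence has four parts.

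*The endpoint is minor.* It sits in a row of section 4 whose stated objective concerns side effects, wounds and breastfeeding, not mood. It is outside the key secondary list that receives false discovery rate control, and no power is claimed for it. This stands, and it limits the severity.

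*The cut has meaning in this protocol.* Thirteen is the protocol's own threshold for notification, and the proportion above it is readily interpreted. Counting women above a threshold and comparing average scores are partly different questions. This also stands: it is a reason to keep the proportion, though not a reason to leave the score unanalysed.

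*The assumed effects may be generous.* The trial is sized on 8.4/15 = 0.56 SD for its direct target, inpatient opioid use. Nothing in the documents supports 0.3 to 0.5 SD on mood six weeks later. For much smaller effects both analyses have little power, and the change would not make an inconclusive result conclusive. This stands.

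*The advantage needs a broad shift.* As shown above, it reverses if only high scorers respond. This stands, and it favours reporting both measures.

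A reader might infer that the comparison is bound to rest on a handful of events and to lose at least half its information. The documents do not support that as fact, because they give no rate: a 20% rate would give 27 events, and a 25% rate 34 events and a 46% loss. Nor do they support the inference that the cut is wrong and should be demoted to a descriptive summary.

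**Conclusion.** The point holds as a cheap improvement of low severity. The documents establish that the scale is collected at 6 weeks, that only the cut at 13 or higher is an endpoint, and that the score is not analysed even though a suitable method is already in the plan. For a shift across the whole score, analysing it would be materially more precise: the cut loses between 78% and 46% of the information at assumed rates of 5% to 25%, and power at 0.4 SD is 15% to 35% against 64%. These figures rest on an assumed rate, score shape, effect and 5% level, none of which the documents supply. Without a broad shift of at least moderate size, the gain may be trivial or reversed. The primary endpoint, its sample size and the key secondary endpoints are unaffected.

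**What to change.** In section 4, add the 6-week Edinburgh total score as a pre-specified secondary outcome. In 8.4.2, assign it to the methods already named there: a between-arm difference with 95% CI from the linear model, or Wilcoxon with the Hodges-Lehmann estimate if the normality condition fails. Keep the proportion at 13 or higher, with its relative risk and CI, as a reported endpoint. Leave the notification rule in 7.2.7 unchanged. Make the change before unblinding.

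The cost is one endpoint line and one model, with no new visit or questionnaire: the notification rule already requires the total and the self-harm item to be scored. The downside is one more secondary comparison. It would sit outside the key secondary list, as the proportion now does, so the false discovery rate adjustment would not change.

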5. STUDY POPULATION

5.1.1 Inclusion Criteria

In order to be eligible to participate in this study, an individual must meet all of the following criteria: Post cesarean delivery (combined vaginal/cesarean deliveries are not eligible)

Singleton, or twin gestation

5.1.2 Exclusion Criteria

An individual who meets any of the following criteria will be excluded from participation in this study:

- Fetal or neonatal death prior to randomization
- Inability to randomize on postoperative day 0
- Inability to complete all three non-invasive bioelectronic treatment during inpatient stay as assessed by research staff
- Language barrier (non-English or Spanish speaking)

• Participation in another intervention study that influences the primary outcome in this trial

5.2 Lifestyle Considerations

There are no lifestyle considerations specific for this study. General post-cesarean instructions will be given to participants during admission and prior to discharge.

5.3 Screen Failures

Screen failures are defined as participants who consent to participate in the clinical trial but are not subsequently randomized to the study intervention or entered in the study. A minimal set of screen failure information is required to ensure transparent reporting of screen failure participants, to meet the Consolidated Standards of Reporting Trials (CONSORT) publishing requirements. Minimal information includes screen failure details, eligibility criteria, and any serious adverse event.

5.4 Strategies for Recruitment and Retention

5.4.1Recruitment Plan

Good recruitment will depend on access, promotion, education and clinical staff buy-in. Research staff will view the daily schedule to review who has had a cesarean. If eligible by medical record review, research staff will approach participants preoperatively or post-operative day 0 to inform them about the study. Randomization should occur on postoperative day 0, but not earlier.

Care providers will be educated about the study via targeted information sessions. It has been found to be helpful to provide in-person informative sessions with specific groups of providers, for example faculty, residents and fellows.

The Ohio State Wexner Medical Center is a large academic medical center with over 5000 deliveries per year. Assuming a 30% rate of cesarean deliveries this is approximately 1500 cesarean deliveries per year. Not every day has 24/7 coverage; therefore it is conservatively assumed that approximately 4 individuals daily are potentially available to enroll on a weekday. It is expected that the number of women who meet the exclusion criteria will be less than 1 percent. Even if 20% of physicians are reluctant to allow their patients to participate (relevant in the setting of private physician deliveries within a hospital) and 60% of women refuse consent for the trial, over 360 women could be enrolled annually.

We are currently conducting a randomized trial in women undergoing cesarean delivery. The aim of the trial is to determine whether an individualized opioid prescription protocol (IOPP) at discharge after cesarean delivery is non-inferior to a prescription for a fixed amount of opioid tablets which approximates current standard of care has similar pain control.

Women are randomized after cesarean delivery and research staff has to be present on day of discharge for randomization. Even with these major barriers to recruitment, sites have been able to recruit approximately 24 participants/ month. While these barriers do not apply to this trial, this study does require a medically trained individual to administer the intervention. Thus the study should conservatively be able to enroll at least 24 participants per month.

6. Study Intervention

6.1 Study Intervention Administration

6.1.1 Study Intervention Description

Women will be randomized on post-operative day 0 to receive treatments with non-invasive bioelectrical device or identical appearing sham device. Three treatments will be given to each patient. The first treatment should be given as soon as is practical after the cesarean section and not longer than two hours after the procedure. The second treatment will be administered 12 hours after the first treatment, but can be given within a range of 10-14 hours after the first treatment to avoid having to wake the patient when sleeping or otherwise disrupt other care being given to the patient. The third and final treatment will be administered 12 hours after the second treatment, but can be given within a range of 10-14 hours after the second treatment, but can be given within a range of 10-14 hours after the second treatment, but can be given within a range of 10-14 hours after the second treatment, but can be given within a range of 10-14 hours after the second treatment, but can be given within a range of 10-14 hours after the second treatment, but can be given within a range of 10-14 hours after the second treatment to avoid having to wake the patient when sleeping or otherwise disrupt other care being given to the patient when sleeping or otherwise disrupt other care being given to the patient.

6.1.1.1 Inpatient opioid consumption (morphine milligram equivalents [MMEs])

Opioid use will be converted to equianalgesic doses of morphine sulfate (morphine milligram equivalents [MMEs]) using standard ratios. Table 1 demonstrates opioid conversions.

Table 1. Opioid Conversion Table

Opioid (mg/day)	Conversion factor
hydrocodone 5mg	1
hydrocodone 20mg	1
oxycodone 5mg	1.5
oxycodone 20mg	1.5

Prior to discharge, participants will complete a brief pain inventory questionnaire. The number of opioid pills prescribed at discharge will be at the discretion of the discharging provider.

6.1.2 Administration

Trained clinic research nurses will apply device three times after cesarean section before discharge (at least 10-14 hrs apart) for duration of 12 minutes each.

6.2 Measures to Minimize Bias: Randomization and Blinding

Selection bias is minimized by the randomized design. However, adequate concealment of the assignment and a clear definition of the point of randomization are also important. Eligible and consenting women will be randomized by certified research staff using a secure internet based randomization system. Once the randomization program has been run by the staff member and the assignment revealed, the participant will be considered randomized even if the woman reneges. Assignment to device or sham device will be in a 1:1 ratio according to a randomization sequence. The simple urn method will be used to generate the randomization sequences because it provides a high probability of balance in treatment assignments, it is unpredictable, and it allows an explicit randomization analysis to be conducted with relative ease.³⁷

Research staff will be responsible for randomization and for administering the intervention or sham device. Clinicians will be blinded to the patient's group assignment.

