2.3.3 Assessment of Potential Risks and Benefits

As described above, potential risks are not more than encountered in usual care after cesarean delivery. Treatment with the TrueRelief device may improve pain control and reduce opioid requirements.

3. Study Design

This is a blinded randomized trial of 134 individuals undergoing a cesarean delivery who are randomized after cesarean to three times use of non-invasive bioelectronic treatment with TrueRelief device or identical appearing sham device for post-cesarean pain management.

The primary endpoint is the total inpatient morphine milligram equivalents used during hospital admission. The primary hypothesis is that three times use of non-invasive bioelectronic treatment with TrueRelief device decreases the total inpatient morphine milligram equivalents used during hospital admission compared to use with identical appearing sham device. Consenting women will be assigned in a 1:1 ratio to one of the two arms using a secure internet based randomization system. Individuals will be followed through 6 weeks postpartum.

4. Objectives and Endpoints

OBJECTIVES	ENDPOINTS		
Primary			
To evaluate whether non-invasive bioelectronic treatment reduces inpatient post-cesarean opioid consumption.	Total inpatient postoperative opioid consumption in morphine milligram equivalents (MME).		
Secondary			
To evaluate whether non-invasive bioelectronic treatment post-cesarean decreases opioid refill prescriptions.	Opioid prescription filled (beyond that prescribed at discharge) between discharge and six weeks postpartum.		
	Total number of opioid prescriptions filled by six weeks postpartum (beyond that prescribed at discharge).		
To evaluate whether non-invasive bioelectronic treatment post-cesarean decreases the total amount of opioid tablets prescribed at discharge.	Number of opioid tablets prescribed at discharge.		
To evaluate whether non-invasive bioelectronic treatment post-cesarean reduces pain intensity pain scores	Pain severity scores (worst, least, average, current) in last 24 hours assessed on the Brief Pain Inventory numeric scale from 0 to 10 at discharge		

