7.2.4 Time Period and Frequency for Event Assessment and Follow-up

Adverse events will be recorded from randomization through 6 weeks postpartum. If a serious adverse event occurs after the consent is signed and before randomization, it will also be reported.

Participants will be instructed to contact research staff to report an adverse event that occurs during study participation. In addition, research staff will ask participants at each study visit if they have experienced any side effects or adverse events since the last study visit.

Adverse and Serious Adverse Events will be reported on the Adverse Event Form.

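### Section 6.2 reveals the assignment to research staff, who also apply the device or sham and ask about side effects; masking is stated only for clinicians

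*Combined protocol and SAP*

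**What the plan says.** Section 3 opens with "This is a blinded randomized trial of 134 individuals undergoing a cesarean delivery" and describes the control as an "identical appearing sham device for post-cesarean pain management". It does not define who is blinded.

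Section 6.2 is the only section on blinding. On randomization: "Eligible and consenting women will be randomized by certified research staff using a secure internet based randomization system". On when a woman counts as randomized: "Once the randomization program has been run by the staff member and the assignment revealed". On delivery: "Research staff will be responsible for randomization and for administering the intervention or sham device". Its one masking statement is "Clinicians will be blinded to the patient's group assignment".

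Section 6.1.2 describes the operators slightly differently: "Trained clinic research nurses will apply device three times after cesarean section before discharge", for 12 minutes each time.

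Section 7.2.4, on adverse events, says "research staff will ask participants at each study visit if they have experienced any side effects or adverse events since the last study visit".

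The documents do not mention device codes, a key holder, a split between the person who randomizes and the person who treats, masked outcome collection, or an unblinding procedure. The sham implies that participants are masked, but this is never stated.

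**The concern.** A sham of identical appearance can mask the woman. It cannot mask an operator who has been told the arm. Here one role learns the assignment, treats the woman at the bedside three times, and later asks about side effects.

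The outcomes are open to influence from that contact. Section 2.3.1 makes opioids available as needed, so total inpatient MME depends partly on what each woman asks for. BPI pain is self-reported. Nausea and constipation are secondary endpoints in section 4. An operator who knows the arm can convey expectation without intending to, and can ask about side effects more or less closely by arm. A difference produced in this way would look like a device effect and could not be separated from one in the analysis.

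**Working it through.** **Who does what, and who is stated to be masked**

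| Task | Role named | Section | Masking stated? |
|---|---|---|---|
| Runs randomization; assignment revealed | Certified research staff | 6.2 | No |
| Applies device or sham | Research staff (6.2); trained research nurses (6.1.2) | 6.2, 6.1.2 | No |
| Asks about side effects and adverse events | Research staff | 7.2.4 | No |
| Completes BPI | Participant | 6.1.1.1 | Implied by sham only |
| Chooses pain medication | Clinical team | 6.3 | Yes, as clinicians (6.2) |
| Judges relatedness of adverse events | Examining clinician | 7.2.3 | Yes, as clinicians (6.2) |

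The first three rows are the gap: one role, three tasks, no masking stated. The last two rows are real protection. Treatment time with an operator is 3 × 12 = 36 minutes per woman (6.1.1, 6.1.2).

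**The plan's own figure**

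Inputs from section 8.2: control mean 42 MME, SD 15, a 20% reduction to 33.6 (difference 8.4), 90% power, 67 per arm. Alpha is not stated; two-sided 5% is assumed.

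- n per arm = 2 × [15 × (1.960 + 1.282) / 8.4]² = 67.01.
- Normal-approximation power at 67 per arm is 0.900; with the t distribution it is 0.896.

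The stated total of 134 is therefore reproduced under two-sided 5%. One-sided 5% would need only 55 per arm (110 in total), so the two-sided assumption fits the plan's number.

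**What a hypothetical expectation shift would do**

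Suppose the device has no effect but operator contact lowers mean use in the device arm by *b* MME.

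- SE of the difference = 15 × √(2/67) = 2.59 MME.
- An observed difference of about 5.1 MME is significant.
- The rejection rate is the two-sided noncentral t probability with 132 degrees of freedom and noncentrality *b*/2.59.

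| Assumed shift *b* (MME) | *b*/SE | Rejection rate |
|---|---|---|
| 0 | 0 | 5% |
| 2 | 0.77 | 12% (0.119) |
| 3 | 1.16 | 21% (0.210) |
| 4 | 1.54 | 33% (0.335) |

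For scale, Table 1 in section 6.1.1.1 gives oxycodone a factor of 1.5. One 5 mg dose is then 5 × 1.5 = 7.5 MME and half a dose is 3.75 MME, so a 4 MME shift is roughly half a dose per woman over the stay. The documents supply none of these shifts. The table shows only how sensitive the test would be if such a shift occurred.

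**The case against.** The strongest reply is that much of this rests on silence, and that several protections are in place.

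- **One person or one role.** A reader might infer that the same individual randomizes, treats and asks the questions. The documents do not say so. Sections 6.2 and 7.2.4 assign tasks to a role, and 6.1.2 calls the operators research nurses. This stands. What remains is that nothing keeps the tasks apart.
- **What the system displays.** A reader might infer that the screen shows device or sham in plain words, because 6.2 uses those words for the assignment. They come from the sentence on the 1:1 ratio, not from the sentence about revealing. A coded device would also be an assignment. This stands as a limit on certainty. Even so, the arm is the natural meaning of a revealed assignment, and no code is mentioned.
- **Contradiction with the blinded label.** Section 3 does not say double-blind. A sham plus blinded clinicians is a coherent design even if operators know the arm, so the label is incomplete rather than contradicted.
- **Protections.** Blinded clinicians control prescribing, under standardized order sets (6.2, 6.3). An operator's influence on MME must therefore pass through the woman's own requests or through disclosure. Women complete the BPI themselves, clinicians judge relatedness, and section 9.1.4 says nearly all form responses are pre-coded. These reduce the risk. They do not reach expectation conveyed to the woman, or how side effects are asked about.
- **Unseen material.** Section 9.1.5 refers to a Manual of Procedures, where masking details may be held. If so, a sentence in 6.2 would settle the matter.

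**Conclusion.** The point holds as a gap in the stated blinding that can be closed cheaply. The research staff role has the assignment revealed to it, delivers the treatment and asks about side effects. Masking is stated only for clinicians, and no safeguard covers the operator. Followed on its natural reading, the plan leaves operators aware of the arm while outcomes that respond to expectation are forming.

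The size is unknown. The 12% and 33% rejection rates rest on assumed shifts of 2 and 4 MME, the planning SD of 15, 67 per arm, a t-test and an assumed two-sided 5% level. A reader might take them as the trial's expected false-positive rate. The documents do not support that, since they give no evidence that any shift occurs or how large it would be. Nor do they show that operators were in fact told the arm in plain terms. The sample size is unaffected.

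**What to change.** In section 6.2, have the randomization system return a masked device code instead of the arm. Use more than one code per arm, so that learning one code does not unmask the whole arm, and let the system or the supplier hold the key. State that participants, operators and those who collect BPI and side effects are masked, and give an emergency unblinding route.

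If operators cannot be masked, say so, script their contact with participants, and have existing staff who do not know the arm collect BPI and side effects.

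If codes are already in use, or the Manual of Procedures already covers masking, one sentence in 6.2 is enough.

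The cost should be small set-up work to code the devices and hold the key. No extra staff are needed, because a sham of identical appearance already exists. The documents do not say how many units are available, so the effort of running several codes per arm should be confirmed. The remaining weakness is that operators may guess the arm if the active output can be perceived.
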